11.5 SAFETY ECG

Individual ECG values will be listed by treatment group in the parent study and visit. They will be summarized using descriptive statistics. Intervals to be provided for each ECG are: respiratory rate, PR, QRS, QT, QT interval corrected, QT interval corrected for Bazett's formula, and QT interval corrected for Fridericia's formula. Post-baseline ECGs will be compared with the baseline ECG. Summary statistics will also be provided for change from baseline in ECG values. The baseline value is defined as the last measurement prior to the first ralinepag dose in APD811-007.

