Abbreviations: 6MWT, 6-Minute Walk Test; BNP, brain natriuretic peptide; ECG, electrocardiogram; hCG, human chorionic gonadotropin; MTD, maximum tolerated dose; NT-proBNP, N-terminal pro-brain natriuretic peptide; NYHA, New York Heart Association; Q3, every 3; QTcB, QT interval corrected for Bazett’s formula; QTcF, QT interval corrected for Fridericia’s formula; RHC, right heart catheterization; RR, respiratory rate; WHO, World Health Organization

^a Reference to pre-dose and post-dose activities in this schedule apply to the morning dose of study drug. Study drug should be taken with food.

^b The Week 25 Visit from Study APD811-003 will serve as the Baseline/Day 1 Visit for Study APD811-007.

- ^c This visit may be conducted by telephone or in person based upon the Investigator's discretion.
- ^d Safety ECG measurements to be completed at Baseline and at Weeks 1 to 9, unless the subject reaches a stable MTD and the subject transitions into the Treatment Period; ECGs will be completed pre-dose and 2 hours post-dose. After the last subject enrolled in Study APD811-007 completes approximately 6 months of treatment and a cumulative all-subject data analysis is performed, as outlined in Section 9, ECGs will subsequently be conducted locally at the discretion of the Investigator (as clinically indicated) during the Q3 monthly visits. The ECG will be performed at the End of Study Visit. Locally collected ECG values for RR, PR, QRS, QT, QTc, QTcB, and QTcF will be collected in the Sponsor's clinical database.
- ^e Clinical laboratory tests will include hematology, serum chemistry, coagulation, and urinalysis. Clinical laboratory tests will be completed pre-dose. After the last subject enrolled in Study APD811-007 completes approximately 6 months of treatment and a cumulative all-subject data analysis is performed, as outlined in Section 9, clinical laboratory tests will subsequently be conducted locally at the discretion of the Investigator (as clinically indicated) during the Q3 monthly visits. A complete clinical laboratory test will be conducted locally at the End of Study Visit. Locally collected laboratory values that are abnormal and clinically significant will be collected in the Sponsor's clinical database along with the reference ranges.

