6.5 ELECTROCARDIOGRAPHY

6.5.1 ECG Equipment

Safety ECGs will be recorded from an ECG machine (12-lead). Safety ECGs will be printed and reviewed on site by the Investigator or designee. Safety ECGs will be captured, recorded, and analyzed according to the Centralized ECG Procedure Manual for visits that require centralized ECG collection (see Table 1 and Table 2).

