6.5.2 ECG Acquisition

Central: The safety ECG equipment will be set according to the procedure manual. The operator will enter certain subject demographic information prior to obtaining the ECG. Every attempt will be made to ensure that subject ECG readings throughout the study will be obtained from the same machine. The following subject information will be entered into the machine:

- Subject initials (example: XYZ or X-Z)
- Subject number (enter the randomization number)
- Subject sex
- Subject date of birth (DDMMMYYYY)
- Study day and time

ECGs will be recorded with subjects in the recumbent position and resting. Subjects will have been in this resting position for 10 minutes prior to ECG recording, and the ECG will be performed prior to any blood draw that occurs at the same time point.

In case of baseline tremor, measures will be taken to eliminate this as it may interfere significantly with the quality of the interpretation. Prior to electrode placement, the anatomical sites will be prepared to allow for proper skin/electrode interface. Subjects with excessive hair will be dry shaven, as needed.

Intervals to be provided on the confirmed read for each safety ECG are: RR, PR, QRS, QT, QTc, QT interval corrected for Bazett's formula (QTcB), and QTcF.

Local: After the last subject enrolled in APD811-007 completes approximately 6 months of treatment and a cumulative all-subject data analysis is performed, as outlined in Section 9, ECGs will subsequently be conducted locally at the discretion of the Investigator (as clinically indicated) during the every 3 (Q3) monthly visits.

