8 GENERAL CONSIDERATIONS FOR DATA ANALYSES

All data included in each data cut will be listed. In general, listings will be sorted by subject number and scheduled assessment (if applicable) or the visit date. Listings will include assessment date, assessment time (if available), and study day. The study day is calculated as the assessment date minus the date of the first ralinepag dose in the APD811-007 study. For data collected on a fixed schedule, the assessment identifier will also be included on the listing.

In general, the data will be summarized by scheduled (nominal) visits. For all presentations of the summary tables, the data will be presented by treatment group of the parent study and overall.

For continuous variables, the summary statistics will include the mean, standard deviation, median, minimum, and maximum. Minimums and maximums will be expressed using the level of precision in which the variable was collected. All other statistics will be rounded, using an additional decimal point. For discrete variables, summaries will include the frequency and

percent in each category. Percentages will be rounded to 1 decimal point. Whenever practical, categories of discrete variables will be ordered and labeled as they appear in the electronic Case Report Form, and all categories represented on the electronic Case Report Form will be included in summaries, even when they do not apply to any subjects in the study.

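### SAP 11.5 pools scheduled ECGs with later local, clinically indicated quarterly ECGs, so late by-visit interval means may not describe the treated population

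*SAP*

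**What the plan says.** **Protocol, collection.** Tables 1 and 2 schedule a 12-lead ECG at every Q3-month visit. Section 6.5.1 says: "Safety ECGs will be captured, recorded, and analyzed according to the Centralized ECG Procedure Manual for visits that require centralized ECG collection". Section 6.5.2 then sets a switch: "After the last subject enrolled in APD811-007 completes approximately 6 months of treatment and a cumulative all-subject data analysis is performed", "ECGs will subsequently be conducted locally at the discretion of the Investigator (as clinically indicated) during the every 3 (Q3) monthly visits". Footnote d to Tables 1 and 2 repeats the rule and adds two things. The final ECG is kept: "The ECG will be performed at the End of Study Visit". Local readings are also retained: "Locally collected ECG values for RR, PR, QRS, QT, QTc, QTcB, and QTcF will be collected in the" sponsor's database.

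**SAP, analysis.** Section 11.5 lists individual values, summarises them descriptively, and says: "Summary statistics will also be provided for change from baseline in ECG values". It mentions visit only for the listing. The by-visit layout comes from section 8: "In general, the data will be summarized by scheduled (nominal) visits". Section 8.4 confirms it, with nominal visits and no windows as the usual rule. Section 8 gives the statistics as mean, SD, median, minimum and maximum; n is not in that list. Sections 7 and 8.2 use all available data and impute nothing. Section 12 mentions local results only for BNP/NT-proBNP and says nothing about ECGs.

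**The concern.** Before the switch, a subject contributes an ECG to a quarterly row because the visit was due. After it, a subject contributes because an investigator saw a clinical reason. The SAP treats the two kinds of record alike, so a late row is partly or wholly a sample of subjects chosen for having an indication. If the reason for the ECG is related to the interval change, the row mean no longer estimates the mean in treated subjects, and it could suggest a long-term trend or conceal one. Readings from different sources may also be combined, both within a row and between baseline and follow-up.

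Long-term safety is the primary objective and ECGs are a named safety endpoint (SAP 2.2). Protocol 1.1.3 reports QTcF increases of 3 to 9 msec at the two highest doses in the first-in-human study. A later healthy-volunteer study found QT prolongation unlikely within its own dose range. Late QTc rows in a long-term study are therefore rows a reader will look at, and a shift of a few milliseconds would matter to that reading.

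**Working it through.** **There is no plan figure to reproduce.** The documents give no ECG mean, SD or expected change, and SAP 6 states that no sample size calculation was made. The check is therefore of the text, followed by an illustration of scale.

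**Step 1: which rows can be affected.** The trigger is one event for the whole study, not a study month for each subject. Let *k* be the months by which a subject's first dose preceded that of the last enrolled subject, and *a* the months from that last subject's 6-month point until the cumulative analysis is done. Scheduled quarterly ECGs then run to about

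6 + *k* + *a* months of that subject's treatment.

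- Last enrolled subject: *k* = 0, so scheduled to about 6 + *a* months.
- A subject enrolled 12 months earlier (assumed, for illustration): scheduled to about 18 + *a* months.
- With *a* = 0, a Month 12 row holds a scheduled ECG from the second subject (12 ≤ 18) and at most a discretionary one from the first (12 > 6).

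Rows up to about 6 months of treatment are therefore unaffected. Later rows can be mixed, and rows beyond 6 + *k* + *a* for every subject are wholly discretionary. The visit label alone does not tell a reader which case applies. The documents give neither *a* nor the spread of *k*. SAP 5 reports an interim analysis in September 2018 but does not say that it triggered the switch, so affected rows cannot be counted.

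**Step 2: does any SAP rule remove or flag these records?**

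| Question | Answer in the SAP |
|---|---|
| Are local ECG values excluded? | No: all available data are used (7, 8.2) |
| Are they a separate stratum or block? | No (11.5; Table 14.3.4.8) |
| Is the change of rule recorded? | No: section 12 covers local BNP/NT-proBNP only |
| Would a shrinking row be visible? | Not necessarily: n is not among the listed statistics (8) |

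**Step 3: scale, under assumptions that are not in the documents.** Take a normal selection model. Let *p* be the share of subjects with an ECG at a visit, *ρ* the correlation between the tendency to be indicated and the true change, and SD the standard deviation of QTcF change. Then

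bias of the row mean = *ρ* × SD × φ(*z*)/*p*, with *z* the (1 − *p*) normal quantile.

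Assume *ρ* = 0, 0.2 or 0.4 and SD = 10 or 20 ms. The subject counts use the protocol's approximate total of 60.

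| *p* (subjects) | φ(*z*)/*p* | *ρ* = 0 | *ρ* = 0.2, SD 10 | *ρ* = 0.4, SD 20 |
|---|---|---|---|---|
| 0.1 (6) | 1.755 | 0 | 3.5 ms | 14.0 ms |
| 0.2 (12) | 1.400 | 0 | 2.8 ms | 11.2 ms |
| 0.5 (30) | 0.798 | 0 | 1.6 ms | 6.4 ms |
| 0.8 (48) | 0.350 | 0 | 0.7 ms | 2.8 ms |

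For example, 0.4 × 20 × 1.755 = 14.0. A negative *ρ* gives the same sizes with the opposite sign. The table shows only how bias depends on coverage and on the link between indication and change. It does not estimate what this study will show.

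**The case against.** The strongest reply is that the table is descriptive, no test depends on it, individual values are listed, and protocol 9.2.1.6 lets a clinically significant ECG change be recorded as an adverse event. A real signal in one subject would not vanish. That stands, and it limits the consequence to how the summary table is read. It does not make the late-row means representative.

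Section 11.5 does not itself say by visit, and the title of Table 14.3.4.8 does not either, unlike several efficacy tables. The general rules in SAP 8 and 8.4 are qualified by words meaning usually. The by-visit layout is therefore an inference, but it is the default and 11.5 sets no exception.

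A reader might also infer more than the documents support:

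- **That every ECG after the switch is selected by indication.** Footnote d keeps the End of Study ECG.
- **That the End of Study ECG exists for everyone and is free of source mixing.** After premature discontinuation, protocol 6.14.1 promises only an attempt at the End of Study procedures. A post-switch End of Study reading may also be local.
- **That local readings are set against a centrally read baseline.** The baseline is the parent study's Week 25 ECG. Section 6.5.1 applies the central manual only to visits that require it, so central reading of the baseline is likely but not stated.
- **That heart-rate means are distorted too.** SAP 11.5 does not list heart rate. SAP 11.4 summarises it from vital signs, which stay scheduled at every Q3-month visit.

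Finally, dropping all late quarterly ECGs would discard information in a long-term safety study. That is fair, and it is why they should stay in the listing and may be summarised separately.

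**Conclusion.** The point holds for the Q3-month ECG rows beyond about 6 months of treatment. Following the SAP as written combines scheduled records with local records obtained for a clinical reason, in a table that serves the primary objective, with nothing to tell the reader. Means and changes for QTc and the other intervals in those rows may not describe the treated population.

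The size is unknown. It is zero if indication is unrelated to ECG change. The 0 to 14 ms range in the working rests wholly on assumed coverage, correlation and SD, and no figure in ms should be quoted as an expected bias. The documents also do not support saying that a QTc trend will in fact be created or hidden. The conclusion rests on reading 11.5 with the general by-visit rule, and on post-switch discretionary ECGs having actually been taken. It is worth correcting before the tables are produced, but it overturns no inferential result.

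**What to change.** Amend SAP 11.5 and Table 14.3.4.8 as follows:

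1. Restrict the by-visit values and changes from baseline to protocol-scheduled ECGs. Apply the filter to each record, by ECG date relative to the switch or by reading source. A cut by visit label will not work, because the switch falls at a different study month for each subject.
2. Add a separate End of Study row, with reading source (central or local) stated.
3. Show n in every row.
4. Keep post-switch discretionary Q3-month ECGs in Listing 16.2.8.7. If they are summarised, use a separate block labelled as local and clinically indicated.
5. In SAP 12, state that the collection rule changed and give the date.

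A worst post-baseline value per subject should not be offered as an unbiased alternative, because it depends on the same selective collection and the same mix of sources.

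**Cost.** The main ECG table loses some late-visit rows, and a small amount of programming is needed. SAP 8 already puts the assessment date in the listings, so a date filter is feasible once the sponsor fixes the switch date. No data are lost and no study procedure changes. It is a cheap improvement.

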12 CHANGES FROM ANALYSIS PLANNED IN THE PROTOCOL

For the final analysis, the following changes have been made to the analyses that are described in the protocol:

- Safety Population will be used for all summaries (protocol Section 9.1 specifies modified Intent-to-Treat Population for efficacy analyses).
- The protocol separated the primary objective and secondary objectives. The analyses will be based on efficacy and safety, not specifically separating the primary and secondary objectives.
- Protocol Section 6.2 states medical and social history would be updated at Baseline in Study APD811-007. These updates were not collected.
- No imputation will be performed for missing efficacy values (protocol Section 9.1 specifies Last Observation Carried Forward imputation for efficacy missing values).
- Baseline for change from baseline in efficacy values will be the APD811-007 baseline value (protocol Section 9.2 specifies the Day 1 pre-dose measurement in Study APD811-003 as the main baseline, with Day 1 of Study APD811-007 as baseline for a secondary analysis).
- Follow-up vital status (mortality) was not collected.
- Local results of BNP/NT-proBNP are not available.

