^c This visit may be conducted by telephone or in person based upon the Investigator’s discretion.

^d Safety ECGs should be completed pre-dose. After the last subject enrolled in Study APD811-007 completes approximately 6 months of treatment and a cumulative all-subject data analysis is performed, as outlined in Section 9 (Planned Statistical Methods), ECGs will subsequently be conducted locally at the discretion of the

- Investigator (as clinically indicated) during the Q3 monthly visits. The ECG will be performed at the End of Study Visit. Locally collected ECG values for RR, PR, QRS, QT, QTc, QTcB, and QTcF will be collected in the Sponsor's clinical database.
- ^e Clinical laboratory tests will include hematology, serum chemistry, coagulation, and urinalysis. Clinical laboratory tests will be completed pre-dose. After the last subject enrolled in Study APD811-007 completes approximately 6 months of treatment and a cumulative all-subject data analysis is performed, as outlined in Section 9, clinical laboratory tests will subsequently be conducted locally at the discretion of the Investigator (as clinically indicated) during the Q3 monthly visits. A complete clinical laboratory test will be conducted locally at the End of Study Visit. Locally collected laboratory values that are abnormal and clinically significant will be collected in the Sponsor's clinical database along with the reference ranges.
 - ^f Serum hCG pregnancy tests will be completed pre-dose at each visit during the Treatment Period. After the last subject enrolled in Study APD811-007 completes approximately 6 months of treatment and a cumulative all-subject data analysis is performed, as outlined in Section 9, pregnancy testing (either serum or urine) will subsequently be conducted locally during each Q3 monthly and the End of Study Visit. Locally collected positive values for hCG will be collected in the Sponsor's clinical database along with the reference range.
 - ^g Vital sign measurements (blood pressure, heart rate, respirations, and body temperature taken in supine position after 5 minutes of rest) will be taken pre-dose.
 - ^h Subjects treated with ralinepag in Study APD811-003 study will continue on current dose.
 - ⁱ WHO/NYHA Functional Class will be assessed pre-dose at all visits.
 - ^j An assessment for further dose escalation or de-escalation will be conducted during the Q3 months.

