6.9 ASSESSMENT OF CLINICAL WORSENING

The Investigator will evaluate the subject for potential clinical worsening throughout the study. If clinical worsening is suspected, additional clinic evaluations may be required to make a final determination as to whether clinical worsening has been met. Clinical worsening is defined as fulfillment of any 1 of the following criteria (as assessed by change from baseline in Study APD811-003):

- Death, or onset of treatment-emergent AE (TEAE) with a fatal outcome occurring less than or equal to 14 days after study treatment discontinuation
- Hospitalization for worsening PAH, heart-lung or lung transplant, or atrial septostomy
- The subject requires the addition (or change in dose if applicable) of any of the following PAH specific medications:
 - Prostacyclin/prostacyclin analogue (IV, SC, oral, or inhaled)
 - PDE5-I or sGC
 - ERA
- The combined occurrence of the events listed below:
 - A decrease in 6MWD by at least 20% from baseline, confirmed on two 6MWTs on different days
 - Increase (worsening) in WHO/NYHA FC from baseline
 - Appearance of or worsening of signs/symptoms of right heart failure that did not respond to optimized oral diuretic therapy

In cases of clinical deterioration, the Investigator must assess carefully if the deterioration of the subject's condition (eg, worsening FC) is related to the underlying PH or can be explained by an alternative cause (eg, transient infection, musculoskeletal disease, surgical or medical intervention other than PH related, exacerbation of a concomitant lung disease, lacking compliance of medication intake). Only persistent clinical deteriorations caused by the underlying PAH and confirmed as per the above criteria will be considered clinical worsening.

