9.2.2 Statistical Analyses of Efficacy Measurements

Efficacy analyses are considered as secondary for this extension study. The time to clinical worsening will be summarized. Estimation and 95% confidence intervals for within-treatment change from baseline in 6MWD, WHO/NYHA FC assessment, and main hemodynamic parameters will also be performed. Baseline is defined as the Day 1 pre-dose measurements from Study APD811-003. A secondary analysis using a definition of Baseline as Day 1 of Study APD811-007 will also be performed.

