8.4 ASSESSMENT WINDOWS

For efficacy and safety assessments, baseline is defined as the last measurement prior to the first dose of ralinepag in the APD811-007 study.

Summary analyses will usually be based on the scheduled (nominal) visits with no visit windows applied. If appropriate, hemodynamic parameters will only be summarized by the Baseline and post-Baseline Visits of APD811-007.

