9.3.2 Baseline Characteristics

Baseline characteristics including 6MWD, 6MWD category (≤440 m versus >440 m), pulmonary vascular resistance (PVR), WHO FC, BNP, and NT-proBNP will be summarized by treatment group in the parent study and overall. Baseline measures are defined as the last measurement prior to the first ralinepag dose in the APD811-007 study.

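### SAP 12 keeps only the APD811-007 efficacy baseline, without a reason, so no listed table shows ex-ralinepag subjects' change since starting ralinepag; the protocol's 95% CIs for within-group change are also left unspecified

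*SAP*

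**What the plan says.** **Protocol.** Section 9.2.2 states: "Baseline is defined as the Day 1 pre-dose measurements from Study APD811-003". It adds a secondary analysis that uses Day 1 of 007. The synopsis entry on efficacy endpoints also ties change in 6MWD, functional class (FC) and hemodynamics to the 003 baseline. Section 9.2.2 asks for interval estimates too: "Estimation and 95% confidence intervals for within-treatment change from baseline in 6MWD, WHO/NYHA FC assessment, and main hemodynamic parameters will also be performed".

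**SAP.** Section 12 states: "Baseline for change from baseline in efficacy values will be the APD811-007 baseline value". The same bullet records what the protocol had specified but gives no reason for the change. Section 8.4 sets the general rule: "For efficacy and safety assessments, baseline is defined as the last measurement prior to the first dose of ralinepag in the APD811-007 study". Sections 10.2 to 10.5 repeat it for each measure. For the baseline characteristics table, Section 9.3.2 says: "Baseline measures are defined as the last measurement prior to the first ralinepag dose in the APD811-007 study".

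**Status at the 007 baseline.** Protocol 7.2.1.1 takes the Week 25 measurements of 003 as the 007 baseline. Table 1, footnote h, says: "Subjects treated with ralinepag in Study APD811-003 study will continue on current dose". Section 5.7 agrees. Ex-placebo subjects start ralinepag only in 007.

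**The concern.** The first ralinepag dose in 007 is the first ralinepag dose ever for ex-placebo subjects, but not for ex-ralinepag subjects. One baseline rule therefore produces two different quantities: change since starting the drug in one arm, and change after Week 25 on the drug in the other.

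The synopsis states the secondary objective as change from baseline with ralinepag treatment. For the group with the longest exposure, the planned tables would answer only the durability question. Sustained benefit would appear as no change, and a reader without the 003 values could take it for no effect.

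The reference points within the report would also differ. Protocol 6.9 judges clinical worsening, including its 6MWD and FC components, against the 003 baseline, while the 6MWD and FC tables use the 007 baseline.

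**Working it through.** The plan has no figure of its own to reproduce here: SAP 6 says that no formal sample size calculation was done. The check is a comparison of texts, followed by an illustration of size.

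**1. What each baseline means by parent arm**

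| Parent arm | 003 Day 1 (protocol main) | 007 baseline (SAP only) |
|---|---|---|
| Ralinepag | before any ralinepag | Week 25, on ralinepag |
| Placebo | before placebo | before any ralinepag |

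**2. Whether another planned table supplies the missing comparison**

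- Baseline characteristics (14.1.5) use the 007 baseline (SAP 9.3.2).
- 6MWD, FC, hemodynamics and BNP/NT-proBNP (14.2.1.2 to 14.2.1.5) use the 007 baseline (SAP 10.2 to 10.5).
- Clinical worsening (14.2.1.1) starts its clock at treatment start in 007 (SAP 10.1).
- The one table whose title spans both studies, 14.1.3, covers exposure.
- On visits, SAP 8.4 says that "hemodynamic parameters will only be summarized by the Baseline and post-Baseline Visits of APD811-007", but only where appropriate.

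No listed table reports efficacy change from 003 Day 1.

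**3. Pooling.** SAP 8 calls for all summary tables by parent group and overall. SAP 10.2 to 10.4 mention only parent group. If the general rule applies, an overall change column averages the two quantities in step 1.

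**4. Size, illustrated with PVR.** Protocol 1.1.3 gives a 20.1% reduction from baseline on ralinepag in 003. Treated as a ratio, the 007 baseline is 1 - 0.201 = 0.799 of 003 Day 1. With c the proportional change from the 007 baseline:

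change from 003 Day 1 = 0.799 × (1 + c) - 1

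| Course after Week 25 | vs 007 baseline | vs 003 Day 1 |
|---|---|---|
| further 10% fall | -10% | 0.799 × 0.90 - 1 = -28.1% |
| fully maintained | 0% | -20.1% |
| 10% rise | +10% | 0.799 × 1.10 - 1 = -12.1% |
| fully lost | 1/0.799 - 1 = +25.2% | 0% |

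For the placebo arm, Protocol 1.1.3 gives a median worsening of 0.7 dyn.s.cm⁻⁵, so the choice of baseline would matter little at the median. The same section reports PVR 29.8% lower than placebo. If that is also a ratio, the placebo arm's own ratio would be 0.799/0.702 = 1.138, a rise of about 14%. The answer for ex-placebo subjects therefore depends on the scale.

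No such figure is available for 6MWD, where Protocol 1.1.3 reports only a numerical improvement, or for FC.

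**5. Confidence intervals.** SAP 8 lists mean, SD, median, minimum and maximum, without n. SAP 10.2 to 10.4 ask for descriptive statistics, shifts and, optionally, geometric means, interquartiles and ratios. The only interval named in the SAP is for the Cox hazard ratio (SAP 10.1). None of the seven items in SAP 12 mentions the within-treatment intervals. For scale, the half-width for a mean change is t(0.975, n-1)/√n in SD units: 0.47 at n = 20, 0.37 at n = 30 and 0.32 at n = 40. These n are assumed; the protocol gives about 60 subjects in total and no split.

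**The case against.** The strongest reply is that SAP 12 is candid. It names the new baseline and both protocol baselines, and what it keeps is the protocol's own prespecified secondary analysis. Protocol 9 requires an explanation only for SAP changes made after database lock, so no stated rule is broken. Efficacy is secondary, the study is open-label without a concurrent control, and change from 003 Day 1 would be an uncontrolled change in selected subjects. All of this stands. It limits the severity, but it does not supply the missing table.

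Some stronger readings are tempting but not supported:

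- *The confidence intervals were dropped.* The SAP never says so. Its preface says that it adds detail to the protocol's analyses, and the list in SAP 8 is not exclusive. They are unspecified, not expressly removed.
- *Hemodynamics are confined to 007 visits.* SAP 8.4 makes this conditional. SAP 10.4 also allows an optional PVR plot over time, though it does not say that 003 data would be included.
- *Ex-placebo subjects lose nothing.* Protocol 4.2 and 7.2.1.1 admit placebo subjects after clinical worsening. Their 007 baseline follows a deterioration, so later change may include recovery or regression to the mean.
- *Exposure is counted only from the parent study.* Table 14.1.2 gives exposure in 007, and 14.1.3 adds the combined figure.
- *The change was made to flatter the results.* The SAP refers to a September 2018 interim analysis and to a May 2019 protocol amendment, but nothing shows why or when the baseline decision was made. In the illustration, the 007 baseline makes a maintained benefit look smaller.

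**Conclusion.** The concern holds in two separate parts. First, an express and disclosed but unexplained departure removes the protocol's main efficacy comparison. For ex-ralinepag subjects, no listed table replaces it. On the illustration, the same PVR course reads about 20 percentage points apart if the benefit is maintained and about 25 apart if it is lost. Second, the SAP is silent on intervals that the protocol promised, and SAP 12 does not list this. It is a gap in specification.

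The change should be made, but the severity is modest: efficacy is secondary and descriptive, and SAP 10.2 to 10.4 present results by parent arm.

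The PVR percentages rest on three assumptions: that the 20.1% behaves as a ratio, which Protocol 1.1.3 does not state; that the arm-level figure applies to those who entered 007; and that the 007 hemodynamic baseline is the end-of-study catheterization of 003. SAP 10.4 makes ratios to baseline optional, so the actual table may show mean or median changes for which these percentages are not exact. The comparison of texts does not depend on them. The conclusion concerns the final-analysis SAP; the documents do not give the content of the interim tables.

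**What to change.** - Add tables of change from 003 Day 1 for 6MWD, FC and hemodynamics by parent arm, beside the 007-baseline tables. Include both arms, because some ex-placebo subjects entered after clinical worsening.
- Footnote them: the change is uncontrolled. For ex-ralinepag subjects it applies to those who completed 003, because Protocol 4.3 excludes the others. For ex-placebo subjects it includes time on placebo, so the 007-baseline table remains their pre-ralinepag comparison.
- In SAP 10.2 to 10.4, specify n and 95% confidence intervals for within-group change. State the form for FC, for example the proportion improved or worsened.
- Exempt change from the 007 baseline from the overall column in SAP 8.
- In SAP 12, give the reason for any departure that remains, including any decision not to produce the intervals.

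The cost is SAP wording and one extra set of tables. The 003 values for 6MWD and FC are already needed to judge clinical worsening under Protocol 6.9. PVR change from baseline was the primary efficacy analysis of 003, and SAP 9.1 already brings parent-study exposure data into the tables.
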